7.3 Preparation and Administration of Protocol-Specified Treatment

All patients will be assigned to receive lucitanib 10 mg daily. The treatment dose may be achieved by combining capsules or tablets of different strengths (see [Section 7.1](#)). Patients should take lucitanib as directed by the treating physician. Lucitanib should be taken with water (240 mL or 8 ounces). Patients should take lucitanib at approximately the same time each day, on an empty stomach, at least 2 hours before and 2 hours after a meal (fasting window is a total of four hours).

Treatment with lucitanib is continuous, but cycles will be defined as 28 days in duration. Dosing will be delayed or modified according to Dose Modification Criteria and Toxicity Management guidelines (See [Section 7.4](#)). Patients are allowed dose reductions by 2.5 mg increments after Cycle 1, Day 1 (C1D1).

Tablets and capsules must be transferred from the bottle to the mouth with minimal manipulations. The investigator will instruct the patient and personnel not to open the capsules; however, in the case of accidental release of the powder from the capsules, contaminated clothing should be removed and washed separately, rubber gloves should be put on, and all contaminated surfaces should be thoroughly cleaned with alcohol, a detergent solution, and then wiped clean with water. Patients should be advised to not suck, chew, or crush the capsules or tablets. Personnel should avoid exposure to crushed and/or broken tablets. In case of accidental skin contact with the content of the capsules or crushed tablets, the area should be flushed with large amounts of water for at least 15 minutes and then washed with soap. Contaminated material should be placed in an appropriate container and sealed before disposal.

If a patient misses a dose but is able to take it within six hours of the intended time, they should be instructed to take the missed dose, on an empty stomach as noted above. However, if the patient is not able to take the missed dose within six hours of the scheduled time, they should skip the missed dose and resume taking lucitanib at the normal time the following day. If a patient vomits the dose within 15 minutes of taking lucitanib, they should take an additional dose. If vomiting occurs more than 15 minutes after taking lucitanib, they should not take another dose until the normal time the following day.

Patients in the PK sub study that vomit after taking lucitanib on Day -7 or Day 1 should not take an additional dose of lucitanib, and PK sample collections should continue per protocol.

The investigator or designee will be responsible for distributing the appropriate strength(s) of lucitanib capsules to patients. A sufficient number of capsules will be provided to the patient to last until the next scheduled visit. Patients will be instructed to record daily doses taken or not taken in a patient diary and will be instructed to bring their lucitanib capsules and diary to the next scheduled visit for reconciliation by site personnel.

7.4 Dose Modification Criteria and Toxicity Management

Patients are allowed dose reductions by 2.5 mg increments after C1D1 (with the exception of patients in the PK sub-study receiving lucitanib on Day -7 and Day 1). Patients are permitted to re-escalate at the start of a cycle by 2.5 mg as long as the cause of the dose reduction has resolved to Grade 1 or better. Dose escalations above 10 mg daily are not permitted.

7.4.1 Hypertension

As observed with other anti-angiogenic anti-cancer therapies, lucitanib can induce or exacerbate hypertension (as described in the Investigator's Brochure). Rapid increases in BP from pre-treatment measurements can be observed as early as the first few days following initiation of therapy. Hypertension can also occur later in the course of treatment.

Hypertension should be closely monitored and treated, if required. Abnormal BP measurements in clinic should be repeated within an hour to confirm findings.

Additionally, patients should be instructed to self-measure their BP at home at least two times per week while receiving lucitanib treatment. Patient-monitored BP should be followed by the investigator at all clinic visits to evaluate the effectiveness of anti-hypertensive treatment.

The early detection and effective management of hypertension are important to minimize risk for the patient and the need for lucitanib dose interruptions and reductions.

The following treatment and lucitanib dose adjustments algorithm should be followed in case hypertension is encountered:

Table 1: Hypertension Guidance Algorithm

Observation	Action

Patient experiences hypertension for the first time or patient with previously controlled hypertension experiences worsening in BP values with SBP from 140 to 159 mmHg and/or DBP from 90 to 99 mmHg.
	
Patients without pre-existing hypertension

	
Initiate anti-hypertensive therapy immediately.
 
Immediate use of two anti-hypertensive agents can be considered in case of rapid elevation of BP. The anti-hypertensive agent can be adjusted over a period of 14 days. The patient should be followed by the investigator at least once a week to evaluate the response to anti-hypertensive treatment. During this period, interruption of lucitanib or dose modification is not necessary.
 
If BP decreases to < 140/90 mmHg within 14 days, continue lucitanib at the same dose.

	
Patients with pre-existing hypertension

	
Intensify/adapt any current anti-hypertensive treatment. Immediate dose and therapeutic class optimization should be performed. Up to three anti-hypertensive agents should be considered.
 
The anti-hypertensive agent can be adjusted over a period of 14 days. The patient should be followed by the investigator at least once a week to evaluate the response to anti-hypertensive treatment. During this period, interruption of lucitanib or dose modification is not necessary.
 
If BP decreases to < 140/90 mmHg within 14 days, continue lucitanib at the same dose.

Observation	Action

In case of persisting hypertension with SBP from 140 to 159 mmHg and/or DBP from 90 to 99 mmHg despite optimized anti-hypertensive treatment after 14 days.
	
Reduce lucitanib dose by 2.5 mg.
 
Ensure adequate control of BP below 140/90 mmHg including increasing the dose of the current anti-hypertensive agent(s) (if appropriate) and/or initiation of additional anti-hypertensive agents, if required.
 
Allow up to 14 days for BP to be controlled. If BP does not reduce to < 140/90 mmHg after 14 days, lucitanib should be reduced again by 2.5 mg (to the next lower dose).
 
Allow an additional 14 days for BP to be controlled.
 
If BP does not reduce to < 140/90 mmHg within the additional 14 days, lucitanib should be interrupted for up to 14 days. If BP decreases to < 140/90 mmHg within 14 days, restart lucitanib at the last dose.
 
If BP remains at \geq 140/90 mmHg after 14 days, sponsor approval is required prior to re-initiating lucitanib treatment.

Observation	Action
In case of confirmed hypertension with SBP equal or above 160 mmHg, and/or DBP equal or above 100 mmHg.	Patients presenting no hypertension-related symptoms & no more than one risk factor¹
	Continue lucitanib therapy. Immediately start anti-hypertensive treatment or optimize current anti-hypertensive treatment. Allow up to 4 days for BP to be controlled (BP < 140/90 mmHg), with close follow-up by the treating physician. If BP does not reduce to \leq 160/100 mmHg within 4 days, lucitanib should be reduced by 2.5 mg. If BP does not reduce to \leq 160/100 mmHg within 4 additional days despite lucitanib dose reduction and optimal anti-hypertensive therapy, lucitanib should be interrupted. If BP decreases to < 140/90 mmHg within 14 days, resume lucitanib at next lower dose. If BP is not controlled (< 140/90 mmHg) within 14 days after interruption of lucitanib and despite optimal anti-hypertensive treatment, lucitanib should be permanently discontinued.

Observation	Action
	
Patients with mildly symptomatic hypertension² (outside of cardiovascular, cerebral, or major renal complications) or several risk factors¹ or already receiving two anti-hypertensive agents
 
Temporarily interrupt lucitanib therapy. Immediate use of two anti-hypertensive agents may be considered in patients with no history of hypertension. For patients already on two anti-hypertensive agents, modification of the current anti-hypertensive therapy and/or adding a third agent should be considered.
 
The patient should be followed by the investigator closely to evaluate the response to anti-hypertensive treatment.
 
Allow up to 14 days for BP to be controlled (BP < 140/90 mmHg).
 
If BP decreases to < 140/90 mmHg within 14 days, resume lucitanib at next lower dose.
 
If BP does not reduce to < 140/90 mmHg within 14 days, lucitanib should be permanently discontinued.

In case of confirmed hypertensive crisis with life-threatening consequences.
 
Hypertensive crisis is defined as an increase in BP (≥ 180 mmHg SBP and/or ≥ 120 mmHg DBP) that can lead to life-threatening consequences (e.g., cerebral stroke).
	
Lucitanib must be permanently discontinued.

¹Risk factors include those comorbidities that in the opinion of the investigator would increase the patient's risk of hypertension-related complications, e.g., diabetes, coronary artery disease

²Mildly symptomatic hypertension defined as symptoms of headache, facial flushing, etc in the absence of additional cardiac or neurological findings

Pharmacological management should be based on the investigator's judgment and no definite recommendations for an anti-hypertensive agent can be made. However, calcium channel blockers may be preferred as initial treatment based on their rapidity of action and safety profile. Angiotensin Converting Enzyme (ACE) inhibitors can be considered in case of concomitant proteinuria [52, 53, 54]. In case of rapid elevation of BP, two anti-hypertensive agents should be

considered. The use of three anti-hypertensive agents, such as concomitant use of a renin-angiotensin system inhibitor, calcium channel blocker, and diuretic drug may be considered based on the investigator's decision. In that case, close surveillance of kidney function and electrolytes is strongly recommended.

Cardiologist and nephrologist advice should be sought when appropriate and especially in the context of associated AEs (i.e., proteinuria, as described below).

Sites should counsel patients on limiting salt intake to less than 4 g/day.

The patient must be educated before the first intake of lucitanib on the importance of BP self-monitoring, trained to recognize signs of hypertension, and to contact the site if BP is greater than 160/100 mmHg at any time.

For purposes of medical history reporting and AE reporting, it is important to strictly follow the National Cancer Institute Common Terminology Criteria for Adverse Events (NCI CTCAE) grading scale, taking into account not only the BP levels, but also the number of anti-hypertensive therapies.

After the withdrawal of lucitanib, the BP must continue to be monitored in order to adjust and progressively stop anti-hypertensive treatments that were started during the study (as appropriate).

Table 2: Grading scale for hypertension (NCI CTCAE Version 4.0)

Grade 1	Prehypertension (SBP 120–139 mmHg or DBP 80–89 mmHg)
Grade 2	Stage 1 hypertension (SBP 140–159 mmHg or DBP 90–99 mmHg); medical intervention indicated; recurrent or persistent (≥ 24 hours); symptomatic increase by >20 mmHg (DBP) or to $>140/90$ mmHg if previously within normal limits; monotherapy indicated
Grade 3	Stage 2 hypertension (SBP ≥ 160 mmHg or DBP ≥ 100 mmHg); medical intervention indicated; more than one drug or more intensive therapy than previously used indicated
Grade 4	Life-threatening consequences (e.g., malignant hypertension, transient or permanent neurologic deficit, hypertensive crisis); urgent intervention indicated
Grade 5	Death

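### Table 1 tells sites both to continue and to interrupt lucitanib in an asymptomatic, low-risk patient on two anti-hypertensives whose BP reaches 160/100 mmHg

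*Protocol*

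**What the plan says.** Protocol Section 7.4.1 tells sites to follow the algorithm in Table 1. For confirmed hypertension of at least 160 systolic and/or 100 diastolic mmHg there are two branches short of hypertensive crisis.

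- **Continue branch.** Heading: "Patients presenting no hypertension-related symptoms & no more than one risk factor". Action: "Continue lucitanib therapy", then "Immediately start anti-hypertensive treatment or optimize current anti-hypertensive treatment". If BP has not come down to 160/100 or below in 4 days, the dose drops by 2.5 mg. If it has still not done so "within 4 additional days despite lucitanib dose reduction and optimal anti-hypertensive therapy, lucitanib should be interrupted".
- **Interrupt branch.** Three alternative entry conditions: mild symptoms, several risk factors, "or already receiving two anti-hypertensive agents". Action: "Temporarily interrupt lucitanib therapy". It adds: "For patients already on two anti-hypertensive agents, modification of the current anti-hypertensive therapy and/or adding a third agent should be considered". If BP falls below 140/90 within 14 days, lucitanib resumes at the next lower dose; otherwise it stops permanently.

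The Synopsis (Dose-Modification Criteria and Toxicity Management) repeats both headings and both actions.

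**The concern.** The continue branch tests symptoms and risk factors only. Because it tells sites to optimize existing treatment, it plainly includes patients already on anti-hypertensives. The interrupt branch treats two current agents as sufficient alone. The two headings therefore overlap, and in the overlap the instructions on study drug are opposite.

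This matters because it is a stop-drug rule for a common toxicity. Section 3.6.1.3 reports worst Grade 3 hypertension in over 50% of pooled patients. Two sites could handle identical patients differently. Since interruptions and dose reductions due to AEs are tabulated (Protocol 11.2.5.2, SAP 17.1), the tolerability summary would also pick up that inconsistency.

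The word *two* raises a side question. Table 1 foresees three agents in its lower BP row ("Up to three anti-hypertensive agents should be considered"). Read strictly as exactly two, the interrupt heading leaves an otherwise identical patient on three agents in the continue branch only.

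**Working it through.** The plan gives no figure to reproduce. The check compares the entry conditions, then the consequences.

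**1. Can the patient occur?** Yes. Exclusion criterion 7 (Section 6.3) bars only patients needing more than two agents, so a patient on exactly two can enroll. On study, Table 1's first row (140–159 and/or 90–99 mmHg) lets sites start two agents at once, or consider up to three in patients with pre-existing hypertension. A patient who then worsens can reach the higher row on two or three agents by following the protocol.

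**2. Does other text settle it?** No.
- Footnote 1 describes risk factors as comorbidities in the investigator's opinion and does not mention the number of agents. Even if two agents counted as one risk factor, a patient with no other would still have no more than one.
- The investigator-judgment sentence after the table concerns the choice of anti-hypertensive drug, not whether to hold lucitanib.
- Neither the remaining text of Section 7.4.1, the synopsis nor Section 7.4.8 gives a precedence.

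**3. Branch membership.** Take symptoms (none, mild) × risk factors (at most one, several) × current agents (0, 1, 2, 3): 2 × 2 × 4 = 16 combinations.
- Continue = no symptoms AND at most one risk factor (4 combinations).
- Interrupt = mild symptoms OR several risk factors OR two agents. The first two conditions alone cover 16 − 4 = 12.

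| Wording | Continue only | Interrupt only | Both | Neither |
|---|---|---|---|---|
| Current, *two* = exactly two | 3 | 12 | 1 | 0 |
| Current, *two* = at least two | 2 | 12 | 2 | 0 |
| Limit added to continue heading only, *two* = exactly two | 2 | 13 | 0 | 1 |
| Limit added, and *two or more* in interrupt heading | 2 | 14 | 0 | 0 |

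The single overlap in the first line is: no symptoms, at most one risk factor, two agents. The second line adds the same patient on three agents. The single unassigned case in the third line is the three-agent patient. These are counts of combinations, not shares of patients.

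**4. Consequences.**
- BP stays above 160/100: the continue branch gives 4 days at the current dose + 4 days at 2.5 mg lower = 8 days before a mandated interruption. The interrupt branch gives 0.
- BP comes under control within 4 days: the continue branch requires no dose reduction. The interrupt branch restarts one dose level lower.

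**The case against.** The best defence is that the intent is clear. The interrupt branch names two-agent patients and gives them their own instruction, while the continue branch refers to current treatment only in general. If the continue branch prevailed, the two-agent condition would bring no additional patient into the interrupt branch. On that view this is an omitted exclusion in one heading, not two equally plausible orders. That is a fair reading of intent, and it shows which way to correct the text. It does not remove the contradiction, because a site that reads the first heading, finds its patient fits and continues dosing has followed the table.

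Three further points affect weight and scope.
- In ordinary usage a patient on three agents is already receiving two, so the three-agent gap exists only on a strict reading. It justifies clearer wording but adds little to severity.
- The grid covers no symptoms or mild symptoms only. A patient with more than mild symptoms short of crisis, at most one risk factor and fewer than two agents meets neither heading now, and would meet neither after the edits.
- The potential harm is limited and unquantified. The over-50% figure pools starting doses of 5 to 30 mg, and Grade 3 also includes needing more than one drug (Table 2). Only 2.6% had a serious hypertension event, and 2.3% discontinued for hypertension. Safeguards exist: repeat measurement within an hour, home BP at least twice weekly, close follow-up in both branches, patient contact with the site for high readings, specialist advice when appropriate, and investigator discretion to stop (Section 12.1).

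**Conclusion.** The concern holds. As written, the row gives opposite study-drug instructions for one reachable kind of patient, in both copies of the algorithm and with no stated precedence. The difference is up to 8 further days of dosing against an immediate stop, assuming BP remains above 160/100 throughout and the site follows the continue branch to its end. Confidence in the overlap is high, because it rests only on the two headings. How often it would arise cannot be estimated from the documents. No endpoint, population, estimate or sample size is affected. It should be fixed as a safety and consistency matter.

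**What to change.** Make both edits in Table 1 and in the synopsis copy:

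1. Add to the continue heading: *and receiving fewer than two anti-hypertensive agents*.
2. Change the last condition of the interrupt heading to: *or already receiving two or more anti-hypertensive agents*.

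Both are needed. With the first alone, an asymptomatic patient with at most one risk factor on three agents would, on the strict reading, have no branch. Within the grid above, the pair leaves no combination in both branches and none unassigned; it does not address more-than-mild symptoms.

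The cost is four heading edits (two per copy) and a notice to sites, with no new procedures or data. The trade-off is that some patients on two or three agents whom sites would have kept on drug will be interrupted and restarted one dose level lower, or discontinued if BP is not below 140/90 within 14 days. For two-agent patients, that is what the table already appears to intend.

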LVEF will be assessed by ECHO or MUGA. It is recommended to use the same technique for a given patient throughout the whole study duration. In case of HF symptoms or modification on imaging from baseline the following rules must be applied:

- No signs of HF and LVEF $\geq 45\%$ OR absolute drop from baseline $\leq 15\%$ EF % points. Continue lucitanib at the same dose level and repeat LVEF assessment per protocol
- Patient is symptomatic OR LVEF $< 45\%$ OR absolute drop from baseline $> 15\%$ EF % points. Hold lucitanib until resolution (LVEF $\geq 50\%$ and asymptomatic). If resolution occurs within 3 weeks, lucitanib can be resumed at a reduced dose by 2.5 mg increments, as described above, otherwise withdraw lucitanib permanently
- No recovery OR LVEF $< 20\%$. Discontinue lucitanib permanently and follow-up the patient

7.4.5 *QT_C prolongation*

In case of CTCAE Grade 3 prolongation of the QT_CF (Fridericia correction) interval > 500 msec, lucitanib treatment must be withheld.

Serum calcium, phosphorus, potassium, and magnesium levels should be analyzed, and levels should be corrected to within normal limits if needed. In all cases a second ECG must be carried out to confirm the QT_CF prolongation > 500 msec within 1 hour of the initial ECG. A review of concomitant medications that could cause QT prolongation and/or Torsades de Points should be performed (see [Section 8](#) and [Appendix C](#)).

Once QT_CF prolongation has resolved, lucitanib may be restarted at a 2.5 mg lower dose. Further dose reductions are permitted, as described above.

Grade 4 QT_C prolongation (QT_C > 501 msec or > 60 msec change from baseline and Torsades de Pointes or polymorphic ventricular tachycardia or symptoms of serious arrhythmia) should result in permanent discontinuation of lucitanib.

7.4.6 *Liver function test abnormalities*

In case of Grade 3 increase in ALT and AST, the dose will be withheld until recovery to Grade 2. If recovery occurs within 14 days, treatment will be resumed at the same dose level. If no recovery occurs within 14 days, the treatment will be resumed at a 2.5 mg lower dose upon recovery. Further dose reductions are permitted, as described above. In case of repeated events at 5 mg or absence of recovery to Grade 2 within 7 days, lucitanib will be stopped permanently.

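### Table 1's only immediate permanent stop for hypertension requires BP of at least 180 and/or 120 mmHg, but the protocol's Grade 4 definition has no BP cut-off, so Grade 4 events at 160–179/100–119 have no mandatory stop

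*Protocol*

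**What the plan says.** Section 7.4.1 of the protocol holds two tables that both describe severe hypertension.

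- **Table 1 (dose algorithm), last row.** Lucitanib is permanently stopped for a confirmed crisis with life-threatening consequences. The row supplies its own definition: "Hypertensive crisis is defined as an increase in BP (≥ 180 mmHg SBP and/or ≥ 120 mmHg DBP) that can lead to life-threatening consequences". The synopsis repeats it.
- **Table 1, row for BP at or above 160/100.** The first branch covers patients without symptoms and with at most one risk factor; they continue lucitanib while BP is treated. The second branch covers mild symptoms ("outside of cardiovascular, cerebral, or major renal complications) or several risk factors"), or patients already on two anti-hypertensive agents. Footnote 2 limits mild symptoms to headache, flushing and the like, "in the absence of additional cardiac or neurological findings". The action is to interrupt, and then: "If BP decreases to < 140/90 mmHg within 14 days, resume lucitanib at next lower dose". If BP is not controlled in that time, the drug is stopped permanently.
- **Table 2 (CTCAE grading), Grade 4.** "Life-threatening consequences (e.g., malignant hypertension, transient or permanent neurologic deficit, hypertensive crisis); urgent intervention indicated". No BP value appears.
- **Reporting.** For medical history and adverse events, "it is important to strictly follow the National Cancer Institute Common Terminology Criteria for Adverse Events (NCI CTCAE) grading scale".

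**The concern.** The stop row is narrower than the protocol's own Grade 4. It covers one of the three examples listed there, and only above a BP threshold. A patient with a transient neurologic deficit at 170/105 is reported as Grade 4, yet does not reach the only row that stops the drug at once and for good.

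The second branch of the 160/100 row deliberately removes cardiovascular, cerebral and major renal complications from its mild-symptom group. Below 180/120 no other row picks those patients up. At stake is re-exposure, after a life-threatening event, to a drug that Section 7.4.1 says can cause or worsen hypertension. The same event at 180/120 is a mandatory stop.

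**Working it through.** No sample-size or error-rate arithmetic applies. The check is to run the written rules on a defined event.

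**One case: a transient ischemic attack at a confirmed 170/105.**

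1. Table 2: Grade 4, because a transient neurologic deficit is listed and no BP level is required.
2. Crisis row: 170 < 180 and 105 < 120, so not met.
3. Row at or above 160/100: met. First branch: fails, because the patient has symptoms.
4. Second branch, mild-symptom limb: fails, because of the cerebral exclusion and footnote 2.
5. Second branch, remaining limbs: met only with several risk factors or two agents already in use. The action is then to interrupt and resume lower if BP is below 140/90 within 14 days, otherwise stop.
6. Without those features, Table 1 gives no action.

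**Grid.** A symptomatic Grade 4 event was run at several BP levels, with 0, 1 or 2 risk factors and 0, 1 or 2 prior agents (3 × 3 = 9 combinations each).

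| BP (mmHg) | No Table 1 action | Only interrupt, resume lower or stop at 14 days | Immediate permanent stop |
|---|---|---|---|
| 165/105 | 4 | 5 | 0 |
| 179/119 | 4 | 5 | 0 |
| 179/120 | 0 | 0 | 9 |
| 180/119 | 0 | 0 | 9 |
| 185/125 | 0 | 0 | 9 |

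The 4 are the 2 × 2 combinations with 0–1 risk factors and 0–1 agents; the 5 are 9 − 4. These counts are rule combinations, not patient frequencies. Moving from 179/119 to 180/119 changes the result from 0 of 9 to 9 of 9. If the exclusion in brackets is read as limiting the whole second branch, a patient with such a complication has no action in all 9 combinations below the threshold.

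Two further facts matter for the wording of a fix. The 160/100 row has no upper limit, so from 180 and/or 120 upward the 5 combinations meet both rows at once. The rows for 140–159/90–99 contain no permanent stop.

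**Rules outside Table 1.**

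- 7.4.4 concerns heart failure and LVEF, so it does not apply to this case.
- 7.4.7 interrupts for suspected PRES and stops permanently only if PRES is confirmed.
- 7.4.8 is written for other Grade 3 or 4 toxicities. If it is taken to apply, it holds the drug until Grade 1, allows restart 2.5 mg lower, and stops by default after more than 14 consecutive days off drug unless investigator and sponsor agree otherwise. A deficit that clears sooner does not reach that stop.
- 12.1 requires discontinuation when the investigator judges the risk unacceptable.

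**Frequency.** Section 3.6.1.3 reports a small number of Grade 4 hypertension events among 230 pooled patients, with no count and no BP. The share below 180/120 is unknown, so the assumption range is 0 to 100%. Serious hypertension was reported in 2.6% (0.026 × 230 ≈ 6). That is context and not a bound, since a stroke or TIA may be reported under its own term. The pooled doses ran from 5 to 30 mg daily, so rates at 10 mg may differ.

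**The case against.** The two tables do different jobs. Strict CTCAE grading is required for reporting, and a reporting grade that is wider than a stopping trigger is not in itself a contradiction. This stands: the point is a gap in the dose algorithm, not an inconsistency in grading.

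The backstops are also real. Under 7.4.8 a stroke that does not recover to Grade 1 within 14 days is stopped by default. Section 12.1 makes the stop mandatory once the investigator judges the risk unacceptable, confirmed PRES is stopped, and 7.4.1 advises specialist input. This also stands, and it narrows the gap to events that recover quickly. It does not close the gap, because the permanent stop below 180/120 still turns on elapsed time, a PRES diagnosis or individual judgement.

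Three stronger readings are tempting.

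- A reader might infer that the protocol intends rechallenge after a stroke or TIA. The bracketed exclusion suggests that the authors did not. The resume instruction follows only from a literal reading of the two-agent and several-risk-factor limbs, and it carries its own stop at 14 days.
- A reader might take the Grade 4 QTc rule in 7.4.5 ("or symptoms of serious arrhythmia) should result in permanent discontinuation of lucitanib") as a precedent for stopping on grade alone. That rule also contains a number (QTc above 501 msec or a change above 60 msec), so it has the same structure as the crisis row.
- A reader might scale the pooled safety data to an expected count in this trial. Without a count, a BP level or rates at 10 mg, the documents do not support any figure, and the number could be zero.

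**Conclusion.** The point holds as a narrow patient-safety gap. For a symptomatic Grade 4 hypertension event at 160–179/100–119, Table 1 gives either no action or, read literally, a conditional instruction to resume at a lower dose. No other section mandates a permanent stop for the event itself. The practical consequence is mainly possible re-exposure after Grade 4 events that recover within 14 days. This rests on the written rules as traced, and on 7.4.8 applying to such events, which is the reading more favourable to the plan.

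The event is rare and its frequency cannot be derived. The PFS analysis is not affected. The two-agent limb is a realistic setting, since exclusion 7 admits patients on up to two anti-hypertensives and Table 1 itself recommends two or three.

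A reader might also infer that stroke, TIA or myocardial infarction at or above 160/100 needs a stop rule of its own. The mismatch between the tables does not support that. Table 2 does not list myocardial infarction, exclusions 5 and 10 govern entry only, and removing rechallenge more widely is a benefit-risk choice for the sponsor.

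**What to change.** At the next amendment, change the last row of Table 1 and its synopsis copy to:

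*Hypertensive crisis with life-threatening consequences, or any CTCAE Grade 4 hypertension (Table 2) regardless of BP level: permanently discontinue lucitanib; this row takes precedence over the rows above.*

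The precedence clause is needed because the 160/100 row has no upper limit. The rules for proteinuria (7.4.2) and LVEF (7.4.4: "If resolution occurs within 3 weeks, lucitanib can be resumed at a reduced dose by 2.5 mg increments") stay as they are.

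The cost is one row in two places, with no extra patients, visits or procedures. The downside is that a few patients (number not derivable) lose the option of rechallenge, including any whose suspected PRES is not confirmed but whose event was graded as Grade 4 hypertension.
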